Protocol: Micronutrient supplementation in children with autism spectrum disorder (ASD): A clinical trial examining mechanism of action

NCT05268744

Background:

Prior studies have suggested that children with developmental disorders including autism spectrum disorder (ASD) have nutritional deficiencies and/or imbalances in vitamins and minerals, including low levels of vitamin D, lithium, zinc, and methionine and high levels of vitamin B6, vitamin C, and beta-carotene, among others.¹ These nutritional deficiencies may be responsible for impaired methylation, decreased glutathione levels, and increased oxidative stress seen in children with ASD.¹

The high prevalence of nutritional deficiencies in ASD may be due to dietary patterns in this population, and multiple studies indicate that children with ASD consume less varied diets with limited fruits and vegetables.² Also, children with ASD have a high prevalence of gastrointestinal symptoms including diarrhea, constipation, and abdominal pain,³ which likely affects the absorption of nutrients and the composition of healthy bacteria in the intestinal tract (microbiome).

There are likely functional consequences to these highly prevalent nutritional deficiencies. One analysis found that autism severity scores were correlated with levels of vitamins, minerals, and amino acids.¹ A double-blind, randomized, placebo-controlled trial of a vitamin/mineral supplement in 141 children with autism found numerous improvements in nutritional biomarkers as well as a statistically significant improvement in parent ratings of child functioning (with specific questions on language, behavior, social function, sleep, gastrointestinal symptoms, and eye contact). The parent rating scale ranged from 1 to 7 (lower scores better), and the children in the treatment group had a 0.34 greater improvement in this score (which was described as a modest benefit). There was no improvement in the Social Responsiveness Scale (SRS) or the Pervasive Developmental Disorder Behavior Inventory (PDD-BI).⁴ A subsequent study from the same group evaluated a more complex intervention that included a nutritional supplement as well as digestive enzymes, carnitine, essential fatty acids, Epsom-salt baths, and a healthy gluten-free, casein-free, soy free diet. The study found improvements in autism symptoms but was limited by the single-blind study design.⁵

Micronutrient supplementation in other developmental disorders, including Attention Deficit/Hyperactivity Disorder (ADHD), have also shown clinical benefits. In a randomized controlled trial of 135 children (mean age 9.8) with ADHD, 54% of children treated with micronutrients were defined as

“responders” on a clinical global impression scale vs. only 18% of children in the placebo group. The treated children also had a small but significantly greater increase in height (6mm), but the parent ratings were not improved in the treatment group.⁶

Several potential mechanisms of action of micronutrients supplementation on improved clinical outcomes have been proposed, including changes in gut microbiota, methylation capacity, and inflammation.⁷⁻⁹ Further clarification of the mechanism of action of micronutrient supplementation has the potential to identify specific pathways involved in clinical benefits and allow for more targeted treatment by screening children for nutritional deficiencies and modifying supplement formulations to optimize benefits. We previously demonstrated the value of using urinary metabolomics to identify physiological changes associated with clinical outcomes in a clinical trial of sulforaphane (an antioxidant supplement) in children with ASD.¹⁰ Fifteen children were enrolled and had a comprehensive urinary metabolomic analysis performed at baseline and after 8 weeks of treatment with sulforaphane. Five metabolic pathways – oxidative stress, amino acid/gut microbiome, neurotransmitters, hormones, and sphingomyelin metabolites were correlated with changes in clinical outcome measures. The sphingomyelin metabolite identification was novel and suggested a possible new line of research to determine whether antioxidant supplementation might alter this important component of neuronal development.¹⁰

Since micronutrient deficiencies are common in children with ASD, and because there is scientific evidence to suggest that supplementation may produce important clinical benefits, we seek to more precisely examine the mechanism of action of micronutrient supplementation through a clinical trial using comprehensive, before-and-after metabolomic analyses. Since the prior study, the metabolomics field has advanced so that it is now possible to obtain metabolomic analyses using Dried Blood Spots (DBS), which are minimally invasive (requiring only a fingerstick and a drop of blood), and provide a much broader metabolomic analysis than urine. We therefore plan to use this new technology in the current study. The analyses may suggest specific metabolic changes that underlie clinical improvements in ASD, which may provide a greater understanding of the physiology of ASD and lead to improved, targeted treatment options.

Methods:

Approvals: The clinical trial will be reviewed and approved by the UCSF Committee on Human Research prior to performing any study activities. The study protocol will be registered at clinicaltrials.gov.

Participants: The UCSF investigative team has an ongoing relationship with a local, non-public school (Oak Hill School, San Anselmo, CA) that specializes in the education of children and young adults with autism and related neurodevelopmental disorders (ages 5-22, grades K-12). This unique academic-school-parent partnership was created with the goal of improving overall care and communication between caregivers, clinical providers, and teachers. All children/families attending the school (n=50 currently) will be invited to participate in the study through e-mail, informational flyers, and an evening informational session.

Children and young adults will be eligible to participate if they are enrolled in the school, have a formal diagnosis of autism, report no use of micronutrient supplements within the last 3 months, are willing to hold other treatments constant for the 8-week study period, have no major medical problems other than ASD, are willing to provide urine samples, and parents were willing to complete on-line surveys at specified intervals. ASD is defined as being present if the child has a diagnosis from a medical professional trained to diagnose autism, or if the student is determined by school staff and the study psychiatrist to meet *Diagnostic and Statistical Manual of Mental Disorders*, Fourth Edition (*DSM-IV*) criteria for ASD. Informed consent will be obtained from the parent/caregiver of all child study participants and directly from all adult study participants. Adults who are conservated will go through an informed consent process and provide assent, and their conservator will be asked to provide informed consent.

Intervention:

The planned study is open-label and all clinicians, parents, and teachers will be aware of the treatment initiation and duration of 8 weeks. All enrolled children will be provided a micronutrient supplementation (EM Power Plus).

Objectives and outcomes:

The primary goal of the study is to determine if any observed changes in symptoms of ASD are correlated with changes in metabolites that occur during treatment with micronutrients. We hypothesize that micronutrient treatment will lead to changes in physiological pathways and that those changes will correlate with clinical improvements.

The two primary outcome measure is the correlation of the changes in clinical symptoms with the change in specific metabolites. Two measures will be used to assess the change in core and associated features of autism: the Autism Behavior Inventory, Short Form (ABI-S) and the Social Responsiveness Scale (SRS). The ABI-S is an observer-reported outcome scale designed specifically to measure change and severity of ASD symptoms and has been shown to have content validity when completed by caregivers.¹¹ The SRS is one of the most commonly used outcome measures in clinical trials of ASD and focuses on social responsiveness and interaction.¹² Parents/caregivers will be asked to complete both measures at baseline, 4 weeks, and 8 weeks using an on-line and secure platform.

Dried blood spots (DBS) will be collected on the day of study initiation and on the final day of the study after the 8-week treatment period. We will be using “batch enrollment” where the parents and caregivers of all potentially eligible participants will be screened for eligibility and asked to go through an informed consent process. Once the final “set” of eligible student participants is identified, they will all be given the study medication and have the DBS sample collected on the same day. DBS is collected using a simple, sterile, finger-prick device and technique, which generates a drop of blood. The participant will be assisted to place his/her finger on a special DBS “card” which will collect the drop of blood. DBS cards will be individually packaged and stored immediately at -80 °C. During the screening visit, children will have a brief physical examination including height and weight to guide the proper dosing. Micronutrient treatment will be provided at the screening visit along with dosing instructions, but participants will not begin the treatment until the study initiation day, when the DBS samples are collected.

Safety assessments:

Parents/caregivers and teachers will be advised to report any concerns about a new medical problem immediately to the study investigators, who will be available at all times to receive reports of possible adverse effects. At the 4 week and 8-week on-line questionnaires, parents/caregivers will be asked to report any new medical problems or concerns for possible side effects.

Metabolomic analyses:

All DBS samples will be sent on dry ice in one batch to Metabolon (Morrisville, NC). Metabolomics analyses will be conducted at Metabolon as previously described ¹³. Briefly, samples will be subjected to methanol extraction, then split into five aliquots for analysis by ultrahigh performance/mass spectrometry in the positive (two methods), negative or polar ion modes. Metabolites will be identified

by automated comparison of ion features to a reference library of chemical standards followed by visual inspection for quality control ¹⁴. For statistical analyses and data display, any missing values will be assumed to be below the limits of detection; these values will be imputed with the compound minimum (minimum value imputation). Data will then be normalized by measured osmolality, which is necessary to reduce the variability ¹⁵. A metabolic pathway for a given metabolite will be assigned based on prior designations in the literature combined with experience from prior datasets at Metabolon.

Statistical methods:

Summary statistics will be used to describe the variables. Change in both the clinical variables and the metabolites will be computed as post-test minus pre-test. Pearson's correlation coefficient will be estimated and tested to index the association between the change in each of the two clinical scales and the change in each metabolite. Given the early-stage nature of the research, we will not adjust for multiple comparisons because we believe it was more important to risk a Type II error than to miss a potentially important signal by being overly conservative, as has been suggested by prior authors ¹⁶.

We define, *a priori*, that a correlation cutoff of an absolute value of ≥ 0.6 is of potential clinical relevance, because, given our planned sample size of 25, we will have approximately 80% power to detect a correlation of that size and such a correlation accounts for roughly one-third of the variance. Others have suggested that correlations with an absolute value of ≥ 0.6 indicate a moderate or higher correlation ¹⁷ (and are hence of greatest interest in pointing to a mechanism of action).

We also plan to examine the number of participants who have a “clinical response,” defined *a priori* as an improvement of 4 or more points in the ABI-S. We will compare the pre-post changes in the ABI-S and SRS in the responder and non-responder groups using the student's t-test.

Planned Data Tables:

Table 1: Characteristics of Enrolled Participants

Category	Characteristic	Subjects N=15	
		%	N
Gender	Male		
	Female		
Ethnicity	White		
	Asian/Pacific Islander		
	No response		
Age	7-10		
	11-14		
	15-21		
	Mean Age		
Primary diagnosis	Autism Spectrum Disorder		
Comorbidities	Intellectual Disability		
	Language Disorder		
	ADHD		
	Pica		
	Global Development Delay		
	Learning Disability		
	Other		
Current meds	Sertraline		
	Lurasidone		
	Risperidone		
	Birth Control		
	Zonisamide		
	Other		

Table 2: Metabolite correlations

Metabolite	Primary Outcome Measure				Metabolic Pathway
	ABI-S Corr.	p-value	SRS Corr.	p-value	
Amino acids (endogenous)					
Benzene metabolism					
Cholesterol metabolism					
Fatty acids					
Monoterpene phenol					
Neurotransmitters					
Oxidative stress					
Polyol					
Sphingomyelin					
Sugars					
TCA cycle					
Other					

Table 3. Change in outcome scores over the 12-week study period

Outcome Measure	Adjusted Mean Scores (95% CI)			Change from Baseline (95% CI)			
	Baseline	1 month	3 months	1 month	p	3 months	p
Autism Behavior Inventory Total Score							
Social Communication							
Restrictive and Repetitive Behaviors							
Mental Health							
Self-regulation							
Challenging Behaviors							
Social Responsiveness Scale Total Score							
Awareness							
Cognition							
Communication							
Mannerisms							
Motivation							

Mean change scores will be adjusted for age and gender; *indicates statistically significant change from baseline

REFERENCES:

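### Eligibility requires willingness to give urine, which the plan never collects, and omits willingness for the two finger-prick blood spots that the primary outcome needs

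*Combined protocol and SAP*

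**What the plan says.** All references are to the combined protocol and SAP.

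- **Methods, Participants (eligibility paragraph).** The only criterion about specimens is that students "are willing to provide urine samples". Blood, finger-prick and dried blood spots are not mentioned in that list.
- **Background, last paragraph.** Dried blood spots are said to "provide a much broader metabolomic analysis than urine", and the plan then commits to them: "We therefore plan to use this new technology in the current study".
- **Methods, Objectives and outcomes.** The primary outcome "is the correlation of the changes in clinical symptoms with the change in specific metabolites". On sampling, the section states: "Dried blood spots (DBS) will be collected on the day of study initiation and on the final day of the study". It adds that "DBS is collected using a simple, sterile, finger-prick device and technique".
- **Methods, Metabolomic analyses.** "All DBS samples will be sent on dry ice in one batch to Metabolon". No other specimen is sent.
- **Background, on the earlier sulforaphane study.** Its participants "had a comprehensive urinary metabolomic analysis performed at baseline and after 8 weeks of treatment with sulforaphane". This is the only urine collection that the document describes, and it belongs to a different study.

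**The concern.** A screener applies an eligibility list as it is written. This list names a specimen that the trial does not use and leaves out the one it does use, so it can go wrong in two ways.

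1. A student who would accept a finger-prick but will not give urine fails a criterion that serves no purpose in this trial.
2. A student who will not accept a finger-prick meets every listed criterion. Metabolite change is computed as post-test minus pre-test, so a participant without both blood spots has no value to enter in the primary correlation.

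There is little slack in recruitment. All participants come from one school, and under batch enrolment the first blood spot and the start of treatment fall on the same day, after the group of participants has been settled. The plan describes no replacement for a student who refuses on that day, no allowance for dropout and no rule for a refused sample. The missing-value rule under Metabolomic analyses attributes missing values to levels below the limit of detection and fills in the compound minimum. That rationale does not fit a card that was never collected.

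**Working it through.** The point is textual, so the main check is to set the sections side by side.

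| Step | Specimen named | Where |
|---|---|---|
| Eligibility | Urine only | Participants |
| Choice of method | Dried blood spots, preferred to urine | Background, last paragraph |
| Collection, both time points | Dried blood spots by finger-prick | Objectives and outcomes |
| Shipping and assay | Dried blood spots | Metabolomic analyses |
| Primary analysis | Change in metabolites, hence both spots | Objectives and outcomes; Statistical methods |

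Apart from the eligibility clause, urine appears only in the account of the earlier study, in the comparison with dried blood spots, and in the titles of references 10 and 15. The eligibility sentence is complete, and no redaction or gap in the text accounts for the mismatch.

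**Recruitment.** The school has 50 students and 25 are planned: 25/50 = 50% must enrol, before any other criterion is applied. The documents give no rate for refusing urine or for refusing a finger-prick, so nothing further can be computed about the pool.

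**Does the point touch the stated power?** Statistical methods gives about 80% power at N = 25 for an absolute correlation of 0.6. It states neither alpha nor sidedness, so I assume two-sided 0.05. By Fisher's z, power = Φ(atanh(r)·√(n − 3) − z), with atanh(0.6) = 0.693 and z = 1.960.

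- n = 25: 0.693 × √22 − 1.960 = 1.29, power 90.2% (91.3% by simulation of the t-test of Pearson's r).
- n = 20: 0.693 × √17 − 1.960 = 0.90, power 81.5% (83.6% by simulation).
- n = 19: 0.693 × √16 − 1.960 = 0.81, power 79.2% (81.4% by simulation).

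The stated 80% is therefore not reproduced at two-sided 0.05; the calculated figure is higher. Other choices of alpha at n = 25 give 94.6% (one-sided 0.05), 82.2% (one-sided 0.01) and 75.0% (two-sided 0.01). That is a separate matter. What matters here is that, under the assumed alpha, losing 5 of 25 pairs, itself a purely illustrative number, would still leave about 82 to 84%. At 0.01 the same loss would leave 70.2% (one-sided) or 61.1% (two-sided), but the documents support neither that alpha nor that loss.

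**The case against.** The strongest reply is that eligibility is not the only gate. Informed consent is required from the parent or caregiver, from adult participants, or from a conservator with the participant's assent. It comes before the group is settled and before any sample is taken. A family that objects to a finger-prick can decline then. A reader might infer that the plan would enrol students who refuse the finger-prick; the documents do not show that. What remains is that a parent's consent does not guarantee a student's cooperation on the day, and that consent does nothing to remove the urine requirement.

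Other replies also have force.

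- The criterion screens on willingness, not ability. It cannot be read as excluding students who are unable to give urine, and whether anyone would in practice be turned away is unknown.
- Any percentage for urine refusal or finger-prick refusal would be invented. Such a rate would also be wrongly applied to all 50 students, since other criteria may exclude some of the same students.
- The consent pages are not in the file, so it cannot be said that they carry the same error.
- The clause may be wording left over from the urinary study. The osmolality normalisation, which cites a urine method (reference 15), is consistent with that. This is an inference, and it does not merge the two points: one concerns data processing and the other enrolment, and correcting one leaves the other in force.

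None of these replies reconciles the eligibility list with the rest of the plan.

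**Conclusion.** The inconsistency is certain from the text: the enrolment rule names a specimen that the trial does not use and omits the one that the primary outcome requires. This is an error in an operative rule, not a questionable design choice, because the Background makes the choice of dried blood spots explicitly.

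Its consequences are possible but cannot be sized. Literal use could exclude a willing blood-spot donor from a small pool, and the list does not screen for willingness to give the two samples that the primary correlation needs; consent partly limits the latter. A reader might go further and conclude that recruitment will fall short or that the trial will be underpowered. The documents do not support either step. They give no refusal rates, and at two-sided 0.05 (assumed) power for a correlation of 0.6 stays above the stated 80% even with 20 pairs. The case for correction rests on the rule being wrong as written, not on power.

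**What to change.** In the eligibility paragraph, replace "are willing to provide urine samples" with: *are willing to provide finger-prick dried blood spot samples at study initiation and at 8 weeks*. Then check that the screening and consent materials agree with the new wording. If urine is in fact intended, keep the clause, add the blood-spot criterion beside it, and describe how urine will be collected and what it will be used for.

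The cost is a one-line protocol amendment. Sample size, visits and analysis do not change unless urine is in fact intended.

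### Non-conservated adults may enrol on their own consent, but the Safety assessments section neither tells participants to report problems themselves nor puts the 4- and 8-week safety question to them.

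*Combined protocol and SAP*

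**What the plan says.** Under Methods, Participants, the source school covers "ages 5-22, grades K-12", and eligibility is not confined to minors: "Children and young adults will be eligible to participate if they are enrolled in the school". The consent rule separates the two groups: "Informed consent will be obtained from the parent/caregiver of all child study participants and directly from all adult study participants". Conservated adults are handled differently: "Adults who are conservated will go through an informed consent process and provide assent, and their conservator will be asked to provide informed consent". The protocol therefore expects that some adults may decide for themselves about taking part.

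The Safety assessments section has two sentences. The first deals with spontaneous reports: "Parents/caregivers and teachers will be advised to report any concerns about a new medical problem immediately to the study investigators". It adds that the investigators are people "who will be available at all times to receive reports of possible adverse effects". The second deals with solicited reports in the 4- and 8-week on-line questionnaires, where "parents/caregivers will be asked to report any new medical problems or concerns for possible side effects".

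Two other places bear on this. The eligibility paragraph requires parents who will complete the on-line surveys. The paragraph on batch enrolment, under Objectives and outcomes, describes only parents and caregivers as being screened and taken through consent.

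**The concern.** Someone who consents for themselves would ordinarily be expected to be told how to report a problem and to be asked whether one has occurred. The Safety assessments section does neither for any participant. Observers can report what they see, or what they are told. A complaint such as nausea or abdominal pain may be invisible to them, and under this section it depends on the adult speaking up without being asked.

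What is at stake is the completeness of adverse-event capture in part of a small cohort (planned sample size 25). The background section also notes that gastrointestinal symptoms are common in autism. That makes it harder for an observer to tell a new complaint from a usual one, and so adds to the value of asking an adult directly. The primary analysis, which correlates metabolite changes with symptom changes, is not affected.

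**Working it through.** There is no figure to reproduce. The check is a comparison of the relevant text.

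1. **Can adults enrol?** Yes. The school's age range reaches 22, young adults are named as eligible, and the top age band of planned Table 1 is 15-21.

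2. **Can some of them consent alone?** Yes. Consent is taken directly from adults, except that a conservated adult assents and the conservator consents. The group at issue is therefore non-conservated adults.

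3. **Who does what for safety?**

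| Task | Parent/caregiver | Teacher | Adult participant |
|---|---|---|---|
| Advised to report new problems | Yes | Yes | Not stated |
| Asked at 4 weeks | Yes | No | No |
| Asked at 8 weeks | Yes | No | No |
| Barred from contacting the investigators | No | No | No |

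4. **Does another section fill the empty cells?** No. Participants are seen on the final day for the second dried blood spot, but no safety question is attached to that contact. No section asks a participant of any age about side effects.

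5. **Which routes remain for a symptom only the adult can feel?** There are three: the adult tells a caregiver, who reports it; the adult tells a teacher, who reports it; or the adult contacts the investigators unprompted. Each depends on the adult raising the matter first.

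6. **How many people does this affect?** The documents give no age distribution and no conservated share. The 15-21 band in Table 1 mixes minors with adults, so even the completed table would not give the number. It cannot be calculated.

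7. **Is the enrolment text consistent with the consent rule?** Not as worded. The batch-enrolment paragraph takes only parents and caregivers through consent, whereas the Participants section also takes it from adults directly.

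**The case against.** The strongest reply is that the plan already has adequate channels. The investigators can be reached at all times, and the text does not limit who may report. Because parents must be willing to complete surveys, every participant, adults included, is meant to have a proxy reporter, and teachers are a second observer. Caregiver report is also how the ABI-S and SRS are collected. The planned Table 1 lists intellectual disability and language disorder among the comorbidities, so reliance on caregivers is understandable. All of this stands, and it is why the point is minor. It does not change the fact that the only solicited safety question bypasses the adult. Proxy report of observed behaviour is also a different matter from proxy-only report of felt symptoms.

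A second reply is that the consent forms may tell adults whom to contact. They are not in the public text, so this cannot be ruled out. Contact details alone would not, however, add the adult to the 4- and 8-week questionnaires, which the Safety assessments section itself assigns to parents or caregivers.

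A reader might also infer several stronger things that the documents do not support:

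- **That adults have no route to the investigators.** Indirect routes exist, and direct contact is not barred.
- **That the safety role contradicts the consent role.** Giving consent and being the named safety informant are different functions, and both sections can be followed as written.
- **That adults are the participants best able to describe side effects.** Nothing in the documents describes their communication ability.
- **That a low event count would be taken as good tolerability.** No tolerability endpoint is defined, and none of planned Tables 1 to 3 reports adverse events.
- **That about 7 of 25 participants are affected.** Ages 18 to 22 are 5 of the 18 year-ages from 5 to 22, and 5/18 = 27.8%, which times 25 is 6.9. This assumes an even age spread that the documents do not give. It also counts conservated adults, so it does not measure the group that consents alone.

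**Conclusion.** The point holds in a limited form. The Safety assessments section states no self-report instruction for participants and puts its 4- and 8-week question only to parents or caregivers, although non-conservated adults can enrol on their own consent. Symptoms that only the adult can perceive may therefore be under-captured.

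Neither the number of such adults nor the number of events that would be missed can be derived from the documents. The conclusion assumes that at least one non-conservated adult enrols, which eligibility permits but does not guarantee. It covers the Safety assessments section only, since the consent forms were not available. It is a worthwhile, inexpensive improvement and does not threaten the trial's main conclusions.

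**What to change.** Amend the Safety assessments section to:

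- tell adult participants, as well as caregivers and teachers, to report new problems directly to the investigators;
- send the existing 4- and 8-week on-line safety question to each adult participant as well as to the caregiver;
- count an event reported by either source, and record the source.

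In the same edit, reconcile the batch-enrolment paragraph under Objectives and outcomes, which mentions only parents and caregivers going through consent, with the direct adult consent set out under Participants.

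The cost is a short text change, a few additional on-line forms, and occasional disagreement between an adult's report and the caregiver's. Recording the source makes such disagreements visible and possible to reconcile. The caregiver questionnaire continues unchanged.

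### No baseline symptom record is described and the week 4 and week 8 safety questions do not ask about worsening, so changes in common pre-existing complaints may be missed or misclassified

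*Combined protocol and SAP*

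**What the plan says.** The Safety assessments section of the combined protocol and SAP sets up two channels.

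- **Scheduled.** "At the 4 week and 8-week on-line questionnaires", "parents/caregivers will be asked to report any new medical problems or concerns for possible side effects".
- **Spontaneous.** Parents, caregivers and teachers are "advised to report any concerns about a new medical problem immediately to the study investigators", who are to be "available at all times to receive reports of possible adverse effects".

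The Background states that "children with ASD have a high prevalence of gastrointestinal symptoms including diarrhea, constipation, and abdominal pain", without giving a percentage.

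The plan describes the following before treatment starts:

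- an eligibility rule that excludes people with a major medical condition besides ASD (Participants);
- a screening contact: "During the screening visit, children will have a brief physical examination including height and weight to guide the proper dosing" (Objectives and outcomes);
- the two clinical scales: "Parents/caregivers will be asked to complete both measures at baseline, 4 weeks, and 8 weeks" (Objectives and outcomes);
- rows for comorbidities and current medication in the Table 1 shell, with no gut row but an Other row in each block (Planned Data Tables).

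The study is open-label and all participants receive the supplement (Intervention). The Statistical methods section does not mention safety, and none of the three table shells reports it.

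**The concern.** Efficacy and safety are handled differently. The ABI-S and SRS are measured before treatment and twice after, and are analysed as change. Safety has the same two later time points but no matching starting point. With no control arm, the only way to judge whether a symptom on treatment differs from the participant's usual state is to know that state.

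The gap matters most for complaints that many participants may already have, and the protocol itself names gut symptoms as common in this population. What is at stake is how reported symptoms can be read: whether worsening is picked up at all, and whether a reported complaint is a change or simply the participant's usual condition.

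**Working it through.** The documents state no safety figure, so there is nothing to reproduce. The check is a reading of the text, followed by one illustration.

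**Step 1: timing.** The scheduled safety questions sit on the week 4 and week 8 questionnaires. The baseline survey is described only as carrying the ABI-S and SRS; no gut or safety item is mentioned.

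**Step 2: wording.** The scheduled question has two limbs. One concerns new medical problems. The other concerns possible side effects and carries no condition of newness. Neither asks directly whether an existing complaint has worsened.

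**Step 3: what the wording does with four cases.**

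| Before treatment | On treatment | Likely handling as written |
|---|---|---|
| Absent | Absent | No report; correct |
| Absent | Present | Reportable as new |
| Present | Worse | Not new; reported only if the caregiver, unprompted, suspects the supplement |
| Present | Unchanged | Should not be reported, but may be if the caregiver suspects the supplement |

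The last two rows are the problem. To tell them apart, the investigator needs to know whether the symptom was present at entry and how severe it was.

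**Step 4: whether other pre-treatment information fills the gap.** The screening examination is brief and its stated purpose is dosing. The eligibility rule removes major conditions, so chronic minor complaints can pass. The comorbidity rows could record a gut diagnosis under Other, but they carry no severity and are not repeated. None of these gives a symptom-level value to set against weeks 4 and 8.

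**Step 5: illustration of size.** Inputs: planned N = 25 (Statistical methods); prevalence *p* of gut symptoms at entry, assumed because the documents give none. Participants with a complaint at entry = 25 × *p*; participants in whom a gut complaint could be new = 25 × (1 − *p*).

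| Assumed *p* | Complaint at entry | Complaint could be new |
|---|---|---|
| 20% | 25 × 0.20 = 5 | 20 |
| 40% | 25 × 0.40 = 10 | 15 |
| 60% | 25 × 0.60 = 15 | 10 |
| 80% | 25 × 0.80 = 20 | 5 |

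The middle column counts participants for whom the last two rows of Step 3 could arise. It does not predict how many would be misclassified; the documents offer no basis for such a rate.

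**The case against.** The strongest reply has five parts.

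1. **Worsening can be reported.** A reader might infer that the plan asks about new problems and nothing else. The text does not support that: the second limb of the question covers possible side effects of any kind, and caregivers and teachers can raise concerns at any time. This stands. The weakness is that nothing prompts for worsening, not that reports of it are shut out.
2. **There is some baseline information.** A reader might also infer that nothing is known before treatment. That too goes beyond the documents, given the screening examination, the eligibility rule and the comorbidity rows. What is missing from the description is a symptom record. The questionnaire items themselves are not reproduced, so the point rests on what the plan describes.
3. **A baseline would not establish cause.** It is tempting to say that the missing baseline is what prevents treatment-related worsening from being identified. In a single open-label arm, a checklist would distinguish new or worse from pre-existing, but would not show that the supplement was responsible. This stands and limits what the fix can claim.
4. **No safety result is planned.** The primary goal is the correlation of symptom change with metabolite change, and no safety objective or analysis is given. This stands as a limit on severity. It does not remove the point, since the plan does collect safety reports and someone will have to interpret them.
5. **The premise is general.** The prevalence statement concerns children with ASD at large, and the Background does not say that supplements aggravate gut symptoms; it reports a controlled supplement trial in which parent ratings, including questions on gut symptoms, improved. This also stands. The point needs only that such complaints may be common at entry and may change during 8 weeks.

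**Conclusion.** The point holds in a limited form. No baseline symptom record is described, the week 4 and week 8 questions do not ask explicitly about worsening, and there is no control arm. Worsening of a common pre-existing complaint may be missed, and an unchanged one may be recorded as a side effect.

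The size depends wholly on how many participants have such complaints at entry: 5 to 20 of 25 across an assumed range of 20% to 80%. The direction of the net error is unknown, because the two kinds of misclassification work in opposite directions. The conclusion assumes that the plan's description of the baseline survey is complete.

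This is a worthwhile and inexpensive improvement to safety detection and classification. It is not a flaw in the primary correlation analysis, which is unaffected.

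**What to change.** - Add one short symptom checklist to the on-line surveys already scheduled at baseline, 4 and 8 weeks. It could cover constipation, diarrhea, abdominal pain, sleep, appetite and other, each with presence and severity.
- Keep the open question and the spontaneous reporting route.
- State in the Statistical methods section that an event is classified as new if absent at baseline and worsened if more severe than at baseline, and that neither label implies that treatment caused it.
- Add one safety table giving, for each symptom, the number of participants affected at each time point and the number worsened.

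The cost is a few more minutes per caregiver at each survey and one extra table; no visit is added. Two side effects should be acknowledged in the report: soliciting symptoms will bring in more minor events, and with a single baseline reading some ordinary fluctuation will be counted as worsening.
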